 - d. Serum calcium great than the upper limit of normal (eg, 10 mg/dl or: 2.5 mmol/l).
 - e. Neutrophil greater than the upper limit of normal (eg, greater than 7.0×10^9 dl).
 - f. Platelets greater than the upper limit of normal (eg, greater than 400 000).
 - g. Lactate dehydrogenase greater than 1.5 times the upper limit of normal.
 - h. Fuhrmann grade of tumour.
 - i. Tumour subtype eg, clear cell vs. non-clear cell.
6. Safety and tolerability reporting for second line axitinib.

The objectives listed below will also be assessed as exploratory analyses for various patient subgroups of interest, and will be conducted if sufficient numbers of patients are available:

1. Axitinib PFS and OS, as a second line therapy following sunitinib, pazopanib, or following other TKIs (eg, sorafenib).
2. Axitinib PFS and OS as a third line therapy.
3. Axitinib (and, if applicable, sunitinib) PFS and OS post-immunotherapy (IO), taking into consideration 2nd and 3rd therapy lines, following all IO therapy options, eg, atezolizumab/bevacizumab, nivolumab/ipilumimab, nivolumab, interleukin-2.

4. For the post-sunitinib axitinib cohort: What was the duration of sunitinib therapy before patients transitioned to axitinib?
5. For the post-pazopanib axitinib cohort: What was the duration of pazopanib therapy before patients transitioned to axitinib?
6. Is the duration of therapy on first line sunitinib and/or pazopanib related to duration of therapy for second line axitinib?

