9.3. Variables

Variable	Operational definition
Demographic details	Anonymised, linked details
Diagnosis Date	Date of diagnosis
Diagnosis	Renal cell carcinoma: clear cell, non-clear cell
Prior surgery eg, nephrectomy	Yes/No; add details as necessary
Line of therapy	1 st line, 2 nd line, 3 rd line
Start date	Start date of therapy
Drug treatment	Drug name
MSKCC Risk Grade	Numeric value, subcategorise if possible: favourable/intermediate/poor risk. Include individual parameters that comprise this grading system where possible
IMDC/Heng Risk Grade	Numeric value, subcategorise if possible: favourable/intermediate/poor risk. Include individual parameters that comprise this grading system where possible
ECOG performance status at outset	Numeric value with related functional level attributed to this
TNM Stage	3 part cancer staging system; provide details where possible
Histology; Fuhrmann grade	Histopathological diagnosis and grading system
Metastasis diagnosis, if applicable	Site and extent of metastatic disease
Response to treatment	PFS, OS, TTD, Best overall response (BOR)
Date of discontinuation	Date of discontinuation of drug treatment
Therapy discontinuation	Reason for discontinuation

Data cut offs	Overall survival, loss to follow-up, withdrawal from study Data cut-off date for OS and PFS is June 2017
Adverse event reporting	It is expected that this data will have been reported through normal mechanisms, and will not have been recorded in the clinical database

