PFS will be measured from the index date of each treatment line to the date of progression, or date of death due to any cause, or date of initiation of new regimen. Patients who are still alive and have not progressed at the last office visit date without clinical or radiographic evidence of progression will be censored (final study cutoff will be June 2017). PFS will be estimated in months using the Kaplan-Meier method with 95% CIs, and summary tables of the number of events and censored patients at each month interval included. Kaplan-Meier plots for PFS will be presented for the overall population and stratified by MSKCC/IMDC risk category (favourable, intermediate, poor). A log rank test will be performed to compare the stratification groups.

Secondary Endpoints

All secondary endpoints will be analysed as follows:

Overall survival (OS)

OS will be defined as the time between the index date (dependent on treatment line) and the date of death from any cause. Patients who are still alive at the study end date or the last visit date available will be censored (using whichever occurred first). If a death date is known beyond the study end date, then the study end date (June 2017) will be used as the censoring

date. Median OS will be estimated in months using the Kaplan-Meier method with 95% confidence intervals (CIs), and summary tables of the number of events and censored patients at each month interval included. Kaplan-Meier plots will be presented for Overall Survival for the overall population, and stratified by MSKCC/IMDC risk (favourable, intermediate, poor). A log rank test will be performed to compare the stratification groups.

Best overall response (BOR)

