TTD will be calculated as the duration between the start of a treatment line to the end of the treatment line for patients with discontinuation of treatment for any reason, or censoring if a stop date is not documented (at end of study), if the patient dies, is lost-to follow up, or is still on-therapy. Patients without a discontinuation event will be censored on the study end date or at last office visit date without clinical or radiographic evidence of progression, whichever occurred first. Time to TTD will be analysed using the Kaplan-Meier method with 95% CIs, and summary tables of the number of events and censored patients at each month interval included.

Durable response rate (DRR)

DRR will be determined as the proportion of patients with objective response (CR or PR) with a duration of at least 6 months. Duration of response will be calculated as previously defined for DOR.

Time-to-Event Analysis

The Kaplan-Meier method will be used to estimate median OS, PFS and TTD. P values comparing survival curves by stratification groups, will be calculated using log-rank tests. Univariate and multivariable Cox proportional hazards regressions will be used to evaluate explanatory factors and to calculate hazard ratios (HRs) with two-sided 95% CIs for OS, PFS and TTD. Demographic and clinical factors will be included in multivariable Cox regression models based on their clinical relevance and/or the univariate significance level (assessed at the level of $p < 0.05$).

In order to account for the impact of baseline patient and disease characteristics outlined in this protocol and the disease characteristics below, unadjusted Cox models and multivariable Cox models adjusting for selected patient demographics and clinical characteristics identified by Pfizer as clinically relevant will be included in the adjusted models. Time-to-event analyses will be assessed in the overall population and by stratifications of interest (MSKCC/IMDC category). The disease characteristics of interest are:

- a. Less than one year from time of diagnosis;
- b. Karnovsky performance status less than 80%;
- c. Haemoglobin less than the lower limit of normal (eg, less than 12 g/dl);
- d. Serum calcium greater than the upper limit of normal (eg, 10 mg/dl or: 2.5 mmol/l);
- e. Neutrophil greater than the upper limit of normal (eg, greater than 7.0×10^9 dl);
- f. Platelets greater than the upper limit of normal (eg, greater than 400 000);

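### The TTD rule censors a line with no documented stop date even when a later line is recorded as started, which biases time on treatment upward

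*Combined protocol and SAP*

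**What the plan says.** Section 9.7 (Time to treatment discontinuation) runs TTD from the start of a line "to the end of the treatment line for patients with discontinuation of treatment for any reason". It then lists the reasons to censor, among them "or censoring if a stop date is not documented (at end of study"). The next sentence sets the censoring date: "Patients without a discontinuation event will be censored on the study end date or at last office visit date" without evidence of progression, whichever came first. Neither sentence mentions a later line, whether as an event, as a substitute stop date or as a limit on the censoring date.

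The same section treats the other endpoints differently. PFS runs to progression "or date of death due to any cause, or date of initiation of new regimen", and the definition of duration of response also includes "or date of initiation of new regimen".

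The variable table in 9.3 collects line of therapy, drug name and "Start date of therapy", and lists the discontinuation date as a separate item. Section 9.6 sends missing data back to the physician for checking against the chart, but accepts that some items will stay unknown. It gives no rule for deriving a missing date.

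**The concern.** Once a patient is recorded as starting axitinib as the next line, first-line sunitinib has ended, and the axitinib start date gives the latest day on which it can have ended. If the sunitinib stop date is blank, the literal TTD rule still censors that line. Kaplan-Meier assumes that a censored patient has the same future risk of the event as those who remain under observation. Here censoring falls on patients whose event has already happened, so events are lost and the curve sits too high.

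Secondary objective 2 reports duration of therapy through TTD in both lines, and secondary objective 5 uses TTD as the outcome when looking for predictive factors. Exploratory objective 4 asks "What was the duration of sunitinib therapy before patients transitioned to axitinib". Every patient in that cohort has stopped sunitinib, so a censored sunitinib duration would make no sense there.

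The point concerns patients known to have switched. How TTD treats death on therapy is a separate matter.

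**Working it through.** **Nothing to reproduce.** The documents state no median TTD, no rate of missing stop dates and no power calculation. What can be checked is the direction of the bias and its size under stated assumptions.

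**Assumed inputs (none from the documents).** Exponential TTD with a true median of 8 months; 30% or 50% of patients with a recorded next line; the stop date missing in 5% to 30% of those. The share of events lost is q = (share with a next line) × (share of those with no stop date).

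**Closed form.** If a share q of discontinuations, unrelated to their timing, is censored at the true stop, the estimated hazard is (1 − q) times the true one, so the estimated median is 8/(1 − q).

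**Simulation.** Each setting used 200,000 patients and the Kaplan-Meier median. Censoring was placed (A) 0 to 3 months before the true stop, as when the last progression-free visit precedes it; (B) at the stop; (C) at a visit well after the switch, using a gap of 0 to 1.5 months plus an exponential time with a median of 12 months.

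| Next line × missing stop date | q | 8/(1 − q) | True median in run | A | B | C |
|---|---|---|---|---|---|---|
| 30% × 5% | 1.5% | 8.12 | 8.05 | 8.16 | 8.18 | 8.22 |
| 50% × 10% | 5% | 8.42 | 7.96 | 8.33 | 8.39 | 8.56 |
| 50% × 20% | 10% | 8.89 | 8.01 | 8.80 | 8.91 | 9.31 |
| 50% × 30% | 15% | 9.41 | 8.02 | 9.26 | 9.43 | 10.12 |

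- q = 1.5%: +1% to +2% against that run's 8.05.
- q = 5%: 8.33/8 to 8.56/8, or +4% to +7%, over A to C.
- q = 10% to 15%, A and B: 8.80/8 to 9.43/8, or +10% to +18%. Under C the increases are +16% and +26%.

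The bias was also upward in every setting with a true median of 6 or 10 months.

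**Upper bound.** If affected patients stayed at risk until study end, the curve would be about (1 − q)S + q. Its median solves S = (0.5 − q)/(1 − q), which gives 8.6, 9.4 and 10.2 months for q = 5%, 10% and 15%.

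**Scale in patients.** Section 9.5 expects about 678 patients on sunitinib and 163 on axitinib, in any line. Even if all were in the line of interest and had stopped, q = 1.5% to 5% means about 10 to 34 sunitinib patients (678 × 0.015; 678 × 0.05) and 2 to 8 axitinib patients (163 × 0.015; 163 × 0.05). q = 15% would need about 102 and 24.

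**Hazard ratios in objective 5.** Under B, an equal lost share in two groups cancels. Unequal shares do not: q = 5% in one group and 1.5% in the other multiplies the hazard ratio by 0.95/0.985 = 0.96.

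**A cohort in which all have switched.** If the TTD rule were applied there, q would equal the missing rate: 10% missing gives 8.76, 8.86 and 9.27 months (A, B, C), and 20% gives 9.70, 9.93 and 10.99.

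**Effect of the repair.** Dating the event at the next-line start gave medians of 7.99 to 8.14 months over 30% to 70% with a next line and 5% to 30% missing, and 8.04 to 8.25 when all had switched. The remainder is the assumed gap plus simulation error.

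**The case against.** **The text may already allow a switch to count.** The plan nowhere says in words that known switchers are censored. The event is the end of the line for any reason, and the end of a line is not defined, so an analyst could treat the next start as that end. This stands as far as it goes. But the only explicit instruction for a missing stop date is to censor, and 9.7 is the whole SAP. Two analysts could report different medians from the same data.

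**Few patients may be affected.** Missing items are queried against the chart. Section 7 lists duration of therapy and the reason for stopping as already collated, and 9.3 includes the discontinuation date. This stands: an affected patient needs a known next line and a stop date that none of these sources supplies. Since 9.6 accepts some residual missing data, the number need not be zero.

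**A stronger reading fails.** A reader might infer from the words in parentheses that a patient who switched years earlier counts as on sunitinib until June 2017. The next sentence does not support that, because the earlier of study end and last progression-free visit governs. For a patient who switched on progression, that visit would normally precede the switch. A switch for another reason could leave later progression-free visits, so some overrun is possible, but study-end censoring is only an upper bound.

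**Exploratory objectives 4 to 6.** A reader might also infer that the rule already produces censored durations there. Section 9.7 does not expressly apply it to them, and they are conditional on numbers. Section 8 does equate duration of therapy with TTD in the secondary objectives, so carrying the rule over would be natural, but that is not stated.

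**Conclusion.** The concern holds. Followed as written, the TTD rule censors lines that the database shows to have ended, while PFS and duration of response in the same section use the start of a new regimen. The direction is upward, including when the censoring visit falls before the true stop.

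The size is not known. It depends on how many stop dates stay missing after query among patients with a recorded later line, which the documents do not give. Under the assumed 8-month exponential median, the increase is roughly 1% to 7% if 1.5% to 5% of events are lost, and roughly 10% to 18% if 10% to 15% are lost with censoring at or near the true stop. The lower range may be the more realistic one, and the effect could be negligible. It touches secondary endpoints, and exploratory ones if the rule is carried over. The primary PFS analysis is unaffected. It should be corrected because the cost is trivial and the dates are already held.

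**What to change.** Add to the TTD paragraph of 9.7:

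> *If no stop date is documented after query but a later line of therapy was started, TTD is an event dated the day before the start of that line. Only patients with neither a stop date nor a later line are censored for a missing stop date.*

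In addition:

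- State that the same end date is used for first-line duration in exploratory objectives 4 to 6.
- Report, by line, how many end dates were derived this way.
- Add a sensitivity analysis using recorded stop dates only.

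The cost is one sentence and one extra table, with no new data. The downside is small: where there is a gap between lines, the derived date overstates time on drug by the length of that gap. The documents give no gap length. With the assumed 0 to 1.5 months, the median moved by at most about 0.25 month, in the setting where all patients had switched and 30% had no stop date. Longer gaps would add more, which the count of derived dates and the sensitivity analysis would help to show.

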7. RATIONALE AND BACKGROUND

Metastatic renal cell carcinoma (mRCC) is a global health problem, resulting in the deaths of more than 14,000 patients every year. Over the past 20 years, there has been a shift from cytokine based therapy towards agents targeting vascular endothelial growth factor (VEGF) receptors, due to the conference of longer progression free survival and overall survival rates with these agents.

Pfizer have two VEGF targeted medicines to treat mRCC: sunitinib and axitinib, and these are used in first and second line respectively. It is important that we have a clear understanding of the real world use and efficacy of our medicines.

The Christie Hospital has been building a detailed database of information regarding patients with mRCC, and now has over 3000 patients' details included.

The information that has been collated includes:

1. Memorial Sloan-Kettering Cancer Center (MSKCC) Criteria (see annex 3.1).¹
2. Heng Criteria (see annex 3.2).²
3. The Eastern Cooperative Oncology Group (ECOG) performance status (see annex 3.3).³
4. PFS.
5. OS.
6. Lines of therapy.
7. Fuhrmann grade (see annex 3.4).⁴
8. TNM Classification of Malignant Tumours (TNM) stage (see annex 3.5).⁵

9. Best response.
10. Stable disease vs partial response.
11. Metastasis diagnosis.
12. Histology.
13. Duration of therapy.
14. Therapy discontinuation due to toxicity/progression.

Although more than 4,000 patients die due to kidney cancer in the UK every year,⁶ in the past 20 years there has been considerable progress in survival outcomes achieved through the delivery of systemic therapy for metastatic and advanced renal cell carcinoma (mRCC and aRCC).⁷ For many years, cytokine therapies including, interferon alpha (IFN- α) and interleukin-2 (IL-2), were the preferred first-line treatments; however, they have been replaced by therapies with longer PFS and OS.⁸

Understanding the abnormal signal transduction pathways in mRCC has enabled the identification and development of molecular targets. For example, loss of the von Hippel Lindau (VHL) tumour suppressor gene leads to upregulated transcription of platelet derived growth factor (PDGF) and VEGF, both of which are major factors in mRCC tumorigenesis (Najjar and Rini, 2012).⁹ As a result of this, there has been a large shift from cytokine based therapy towards agents targeting VEGF pathways, and in particular tyrosine kinase inhibitors (TKIs).

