8. RESEARCH QUESTION AND OBJECTIVES

Research Questions:

To understand the clinical outcomes of patients treated with sunitinib in first line and axitinib in second line in a real world setting as therapies for mRCC and/or aRCC.

Primary Objective:

1. What is the PFS of patients treated in first line with sunitinib, and stratified by MSKCC/IMDC risk category (favourable, intermediate, poor)?
2. What is the PFS of patients treated in second line with axitinib, and stratified by MSKCC/IMDC risk category (favourable, intermediate, poor)?

Secondary Objectives:

First Line:

1. What is the OS of all patients in first line with sunitinib, and stratified by MSKCC risk (favourable, intermediate, poor)?
2. What is the duration of therapy with sunitinib in first line (using time TTD) for all patients and stratified by MSKCC risk (favourable, intermediate, poor).
3. ORR.
4. Duration of ORR (CR or PR).
5. Examine factors that predict duration of therapy on sunitinib (TTD), eg, risk stratification, or individual/grouped parameters that comprise the prognostic classification systems.
 - a. Less than one year from time of diagnosis.
 - b. Karnovsky performance status less than 80%.
 - c. Haemoglobin less than the lower limit of normal (eg, less than 12 g/dl).
 - d. Serum calcium great than the upper limit of normal (eg, 10 mg/dl or: 2.5 mmol/l).
 - e. Neutrophil greater than the upper limit of normal (eg, greater than 7.0×10^9 dl).
 - f. Platelets greater than the upper limit of normal (eg, greater than 400 000).
 - g. Lactate dehydrogenase greater than 1.5 times the upper limit of normal.
 - h. Fuhrmann grade of tumour.
 - i. Tumour subtype eg, clear cell vs. non-clear cell.
6. Safety and tolerability data reporting for first line sunitinib.

Second line:

1. What is the OS of all patients in second line with axitinib, and stratified by MSKCC risk (favourable, intermediate, poor)?
2. What is the duration of therapy with axitinib in second line (using TTD) for all patients and stratified by MSKCC risk (favourable, intermediate, poor).
3. ORR.
4. Duration of ORR (CR or PR).
5. Examine factors that predict duration of therapy on axitinib (TTD), eg, risk stratification, or individual/grouped parameters that comprise the prognostic classification systems.
 - a. Less than one year from time of diagnosis.
 - b. Karnovsky performance status less than 80%.
 - c. Haemoglobin less than the lower limit of normal (eg, less than 12 g/dl).

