9.6. Data Management

Participants will be pseudo- anonymised by the assignment of a unique patient identification number to each record.

Data will be transferred using a secure data transfer to Pfizer, which satisfies the Pfizer secure data transfer requirements, and allows an audit trail. There will be a data validation step to ensure all data have been transferred successfully.

Any missing or illegible data on any patient will result in Pfizer contacting the physician with the anonymized-linked identifier and submitting the form for validation of the missing data against the patient's medical chart. However, certain information may not be available in charts, in which case it will be described as unknown/ missing.

All work will be subject to quality control and documentation procedures to make certain the report is accurate and thorough, and the analyses can be reproduced.

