In prospective clinical trials, BOR is generally assessed according to the Response Evaluation Criteria In Solid Tumours (RECIST) 1.1.¹³ However, the parameters underlying these criteria are less reliably available in retrospective, observational studies. While an attempt will be made to mimic the RECIST guideline, it should be noted that assessments based on information garnered during routine clinical practice could be more subjective than assessments in a controlled clinical trial and decision making about continued therapy could include symptomatic criteria. Additionally, timing of repeat imaging may vary. All evaluation in this observational study will be as best determined by clinicians, either as noted in the patient chart by the radiologist-written scan report or the treating physician's progress notes or as interpreted by the clinician reviewer. The BOR for a line of treatment is the best response across all timepoints during that line of therapy assessed using the following categories: Complete response (CR), Partial Response (PR), Stable Disease (SD), Progressive Disease (PD), Not Evaluable (NE).

Objective response rate (ORR)

BOR will be summarized as ORR, which is defined as the number of patients having reached a BOR of CR or PR divided by the number of patients (the primary analysis population), including the NE patients.

ORR = Number of patients achieving a response (BOR = PR or CR)/Number of patients (BOR=CR+PR+SD+PD+NE).

Patients who do not have a BOR assessment for a particular line of therapy will be excluded from the summary for that line of therapy. The number of patients with a missing BOR assessment will be summarized.

Duration of response (DOR)

DOR will be calculated for each patient with a BOR of CR or PR as the duration of time from first documented CR/PR, to the earliest date of first progression or recurrent disease, or date of death, or date of initiation of new regimen. Patients who are still alive and did not progress will be censored at the last physician office visit date without clinical or radiographic evidence of progression. DOR will be estimated in months using Kaplan-Meier method with 95% CIs, and summary tables of the number of events and censored patients at each month interval included.

Time to treatment discontinuation (TTD)

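### Because deaths on treatment are censored, the planned TTD analysis does not estimate duration of therapy

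*Combined protocol and SAP*

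**What the plan says.** - **Purpose.** Section 8, first-line secondary objective 2, asks "What is the duration of therapy with sunitinib in first line (using time TTD) for all patients". The second-line objective asks the same for axitinib. Objective 5 in each line looks for predictors of duration of therapy, again identified with TTD.
- **Event and censoring.** Section 9.7 measures TTD from start to end of the treatment line, with stopping for any cause as the event. The same sentence provides for "censoring if a stop date is not documented (at end of study), if the patient dies", and adds loss to follow-up and ongoing therapy.
- **Censoring date.** Patients with no event are "censored on the study end date or at last office visit date without clinical or radiographic evidence of progression, whichever occurred first". The date of death is not named as a censoring date.
- **Analysis.** Kaplan-Meier medians, log-rank tests by risk group, and Cox models.
- **Other endpoints.** In Section 9.7, PFS ends at "date of progression, or date of death due to any cause, or date of initiation of new regimen". DOR ends at progression or recurrence, "or date of death, or date of initiation of new regimen".
- **Data.** Section 9.3 collects "Date of discontinuation of drug treatment" and an open reason field. Section 7 describes the existing database item as "Therapy discontinuation due to toxicity/progression". Neither says how a death on drug is entered.

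**The concern.** Duration of therapy is a complete, known quantity for a patient who dies on drug. Censoring that patient treats the end of therapy as unknown and assumes the patient would have gone on to stop at the rate of those still treated. The resulting curve describes stopping in a setting where nobody dies, which is not the question in Section 8. A cause-specific analysis could be chosen deliberately, but the plan neither names that estimand nor adds a competing-risk analysis. That PFS and DOR count death as an event does not prove an error here, but it shows that the plan can treat death explicitly.

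The rule is also ambiguous. A death with a stop date entered at or near it is an event under the first half of the sentence and censored under the second. Two programmers could code it differently.

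Affected are secondary objectives 2 and 5 in both lines and exploratory objective 6, which relates first-line duration to axitinib duration. The planned monthly tables of events and censored patients would not separate deaths from other censoring.

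**Working it through.** The plan gives no TTD figure and no count of on-treatment deaths, so there is nothing to reproduce and every input below is an assumption, except the patient numbers.

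**Inputs.** p = share of treatment endings that are deaths with no recorded stop (5, 10, 20%). L = months from the censoring visit back from death (0, 3, 6). All-cause median time on drug 8 months, constant hazard h = ln 2/8 = 0.0866 per month.

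**Formula.** Stops occur at rate h(1-p)S(t). Patients who will die within L months have already left the risk set, which is therefore S(t)[1-p+p·exp(-hL)]. The Kaplan-Meier hazard is the ratio of the two, so

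reported median / true median = 1 + [p/(1-p)]·exp(-hL).

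With exp(-3h) = 0.771 and exp(-6h) = 0.595:

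| p | L = 0 | L = 3 | L = 6 |
|---|---|---|---|
| 5% | 1.05 | 1.04 | 1.03 |
| 10% | 1.11 (8.9 months) | 1.09 (8.7) | 1.07 (8.5) |
| 20% | 1.25 (10.0 months) | 1.19 (9.5) | 1.15 (9.2) |

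Simulation (400,000 patients per cell, cutoff 1 to 120 months after line start) gave 1.110/1.083/1.066 for p = 10% and 1.250/1.191/1.151 for p = 20%.

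**Sensitivity to shape and timing, p = 20%, L = 0/3/6 (simulated).** Weibull shape 0.8: 1.32/1.26/1.21. Shape 1.3: 1.19/1.14/1.10. All deaths before month 8: 1.40/1.35/1.33. All deaths after month 8: 1.00/0.98/0.95.

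**Direction.** If censoring is at the date of death, events become censorings at the same times, which can only raise the curve or leave it unchanged. With the planned visit anchor this guarantee is lost. Take two patients: A was last seen progression-free at month 1 and dies on drug at month 10; B stops at month 5. Under the plan A is censored at month 1 and the curve falls to 0 at month 5. With death as an event it is 0.5 from month 5 to month 10.

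**Risk groups.** Assume true medians of 12 and 6 months (ratio 2.0). With p = 5% in the favourable group and 20% in the poor group, the reported ratio is 1.68/1.77/1.84 for L = 0/3/6; at L = 0 this is 2.0 × 0.80/0.95. With p = 20% and 10% it is 2.25/2.24/2.23. The direction depends on unknown shares.

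**Against sampling error.** Section 9.5 expects about 678 sunitinib and 163 axitinib patients. If all were in the relevant line and uncensored, the 95% half-width of the median would be 1.96/(ln 2·√n): 0.109 and 0.221. The bias reaches these values at p of about 10-15% and 18-27% respectively (L from 0 to 6).

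**The case against.** The strongest reply is that the bias depends on something unknown. If a stop is recorded at or before death and counts as the event, the bias is zero. Section 9.6 says that "Any missing or illegible data on any patient will result in Pfizer contacting the physician", which should reduce missing stop dates. At p = 5% the effect is 3-5%, well inside the sampling error. All of this stands, and it limits what can be said about size. It does not repair the rule: the plan does not say that a recorded stop overrides the death clause.

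A reader might infer that the TTD hazard ratios are simply wrong. The documents do not support that. A Cox model that censors a competing event when it occurs estimates the cause-specific hazard of discontinuation, a recognised quantity for predictors, and the title-page objectives speak of factors that predict TTD. What remains is that Section 8 equates TTD with duration of therapy for the same objective, and a cause-specific ratio for discontinuation is not a ratio for time on drug.

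Reason for stopping is collected and, under the descriptive plan in Section 9.7, should be tabulated with missing values as a category. That may reveal some on-treatment deaths, but it does not change the estimator.

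Finally, using death as the stop date whenever no stop is recorded has its own upward bias. If 10% of endings are undated stops with no next regimen, and death follows a median of 6 or 12 months later, that approach gives about 1.09 or 1.12 times an 8-month true median, against 1.11 under the current rule if censored at the stop. This stands, and the fix below allows for it.

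**Conclusion.** The point holds as a mismatch between the TTD rule and the question it is meant to answer, with an unresolved overlap between the event and censoring clauses. It should be fixed before analysis. Confidence is high on the reading of the rule and low on the size of the effect.

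Under the constant-hazard assumptions, overstatement is about 3-5%, 7-11% and 15-25% for shares of 5, 10 and 20%. Other hazard shapes and death timings at 20% range from 5% too low to 40% too high. Two stronger inferences are not supported: that the median must be overstated, because the progression-free-visit anchor usually shrinks the bias and can reverse it; and that any particular overstatement will occur, because the share of deaths without a stop date is nowhere given.

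PFS and OS are unaffected. Prior-therapy duration in exploratory objectives 4 and 5 is not touched by the death rule, because those patients lived to start axitinib.

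**What to change.** 1. Define the TTD event as the earliest of a documented stop date, the start of the next regimen, or death while known to be on that drug. State that a recorded stop takes precedence over the death rule.
2. Censor patients not known to have stopped at the last date known to be on the drug, up to the June 2017 cutoff.
3. For patients who died with no stop date and whose treatment status stays unknown after the chart query in Section 9.6, report the number by line and risk group. Show the median both ways: event at death, and censored at the last date known on drug. A death date used as a stop date can add off-drug time, so neither version alone is safe.
4. Keep the current rule only as a sensitivity analysis labelled as cause-specific discontinuation with death censored, and state there how a stop date at or near death is coded.

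**Cost.** One definition change, one count table and one or two extra runs. Start date, stop date, stop reason and survival data are already listed in Section 9.3. The last date known on drug may need visit records, as the present rule already does. Start of the next regimen can also include some off-drug time, so the number of patients relying on it should be shown. Section 9.7 is not consistent on the formalities: its opening paragraph calls for an amendment for any major change to the analysis plan, while its closing paragraph speaks only of primary endpoint definitions and their analyses. The sponsor should settle which applies to a secondary endpoint.
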